6.6 Dose modification and discontinuation

Specific guidance for the management of AEs, including interruption or reduction of treatment with selumetinib, may be considered for particular events of special interest (i.e. diarrhoea, dyspnoea, rash, asymptomatic reduction in LVEF, and visual disturbance), as indicated in the algorithms provided in Appendix E. Oral care recommendations are also provided in Appendix E. Some AEs (hyperphosphatemia and increase in calcium phosphate) should be managed according to local practice.

For all AEs reported in this study that are considered at least partly related to administration of selumetinib, the following dose reduction/adjustment guidance should be applied unless otherwise specified in the Guidance for management of specific AE (Appendix E):

- Treatment with selumetinib should be temporarily interrupted if one of the following AEs occurs and is considered related to treatment with selumetinib:
 - Any intolerable AE regardless of grade.
 - Any AE CTCAE grade 3.

On improvement of the AE to CTCAE grade 1 or less within 4 weeks of onset, study treatment may be restarted at a reduced dose at the discretion of the investigator. Twostep dose modification is applied in the study (see Table 7). Any subjects with 2 prior dose reductions who experience a toxicity that would cause a third dose reduction must be discontinued from study treatment.

Body surface area (m ²)	Selumetinib dose (mg) ^a Dose level 0		First selumetinib dose (mg) reduction		Second selumetinib dose (mg) reduction ^b	
	AM	PM	AM	PM	AM	PM
0.55 to 0.69	20	10	10	10	10 mg once daily	
0.7 to 0.89	20	20	20	10	10	10
0.9 to 1.09	25	25	25	10	10	10
1.1 to 1.29	30	30	25	20	20	10
1.3 to 1.49	35	35	25	25	25	10
1.5 to 1.69	40	40	30	30	25	20
1.7 to 1.89	45	45	35	30	25	20
≥1.9	50	50	35	35	25	25

Table 7Two-step Dose Modification Procedure

- ^a Actual dose in mg (capsule sizes 10 and 25 mg) administered every 12 hours to achieve a dosage of 25 mg/m² twice daily.
- ^b Permanently discontinue selumetinib in patients unable to tolerate Selumetinib after two dose reductions.
- If a different AE subsequently requires dose interruption, appropriate selumetinib dose modification should be considered on improvement of the AE at the discretion of the investigator, in line with Table 7.
- The dose may be increased to account for an increase in BSA at the time of on study evaluations.

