Treatment with selumetinib should be permanently discontinued for any CTCAE grade 4 toxicity that is at least partially related to selumetinib. However, if it is felt to be in the best interest of the subject, interruption of Selumetinib with potential to restart at a reduced dose upon resolution to grade 1 or less may be considered on a case-by-case basis for CTCAE grade 4 AEs in consultation with the study physician.

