7.3 Withdrawal from the study

A subject may withdraw from the study (e.g. withdraw consent), at any time (IP **and** assessments) at his/her own request, without prejudice to further treatment.

A subject who considers withdrawing from the study must be informed by the investigator about modified follow-up options (e.g. telephone contact, a contact with a relative or treating physician, or information from medical records) per Section 7.1.3.

If the subject or his/her parent(s)/legal guardian withdraws consent for disclosure of future information, the sponsor may retain and continue to use any data collected before such a withdrawal of consent.

If a subject or his/her parent(s)/legal guardian withdraws from the study, he/she may request destruction of any samples taken, and the investigator must document this in the site study records.

A subject who withdraws consent will always be asked about the reason(s) and the presence of any AE. The investigator will follow up subjects as medically indicated.

AstraZeneca or its delegate will request investigators to collect information on subjects' vital status (dead or alive; date of death when applicable) at the end of the study from publicly available sources, in accordance with local regulations. Knowledge of the vital status at the end of the study for all subjects is crucial for the integrity of the study.

See Table 1 for data to be collected at the time of study discontinuation and follow-up and for any further evaluations that need to be completed. All study treatment and treatment diaries should be returned by the subject.

Study procedures and their timing are summarised in Table 1.

The investigator will ensure that data are recorded in the eCRFs. The Web Based Data Capture (WBDC) system will be used for data collection and query handling.

The investigator ensures the accuracy, completeness, legibility, and timeliness of the data recorded and of the provision of answers to data queries according to the Clinical Study Agreement. The investigator will sign the completed eCRFs. A copy of the completed eCRFs will be archived at the study site.

Immediate safety concerns should be discussed with the sponsor immediately upon occurrence or awareness to determine if the subject should continue or discontinue study treatment.

Adherence to the study design requirements, including those specified in Table 1, is essential and required for the conduct of the study.

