Grade 4	Life-threatening consequences; urgent intervention indicated.
Grade 5	Death.

E 5 Management of New or Worsening Dyspnoea

Table 18CTCAE (version 5) grading for pneumonitis

CTCAE term	Grade 1	Grade 2	Grade 3	Grade 4	Grade 5
Pneumonitis	Asymptomatic;	Symptomatic;	Severe	Life-threatening	Death
	clinical or	medical	symptoms;	respiratory	
	diagnostic	intervention	limiting self	compromise;	
	observations	indicated;	care ADL**;	urgent	
	only;	limiting	oxygen	intervention	
	intervention not	instrumental	indicated	indicated (e.g.,	
	indicated	ADL*		tracheotomy or	
				intubation)	

*Instrumental ADL refer to preparing meals, shopping for groceries or clothes, using the telephone, managing money, etc.

**Self care ADL refer to bathing, dressing and undressing, feeding self, using the toilet, taking medications, and not bedridden.

E 6 Management of subjects with rash

Severity	Management STEP 1	Management STEP 2
CTC Grade 1 or 2 Tolerable Rash	Continue Selumetinib treatment and monitor as clinical indicated.	-
	Manage rash as per paediatric or adult treatment recommendations.	
CTC Grade 2 Intolerable or CTC Grade≥3	Consider Selumetinib dose interruption. Consider referral to a dermatologist. Manage rash as per paediatric or adult treatment recommendations.	If rash has improved to Grade 2 tolerable or less within 4 weeks, re-start selumetinib at original dose or consider reduced dose.

Table 19Management of Rash

Tabla 20	Rash - Pandiatric Treatment Recommendation	•
		13

Severity	Treatment Recommendations	Note
CTC Grade 1 Rash	Apply a mild potency topical steroid* and topical antibiotic**.	*Topical steroids e.g: 1% hydrocortisone or desonide cream for
CTC Grade 2 Rash (Tolerable)	Apply a moderate potency topical steroid* and initiate an oral antibiotic***.	the face or 0.1% triamcinolone cream for the body (do not use on the face).
	Topical antibiotics should be discontinued before initiation of oral antibiotics.	**Topical antibiotics e.g: 1%

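### The rash restart rule in Appendix E, Table 19 has no upper grade limit, and it is unclear whether it displaces the Grade 4 safeguards in Section 6.6

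*Protocol*

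**What the plan says.** Two places in the Protocol deal with restarting selumetinib after a severe related rash.

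**Appendix E, E 6, Table 19.** The lower row is labelled "CTC Grade 2 Intolerable or CTC Grade≥3". Its first step asks the site to consider interrupting selumetinib and to consider a dermatology referral. Its second step reads: "If rash has improved to Grade 2 tolerable or less within 4 weeks, re-start selumetinib at original dose or consider reduced dose". Table 22, which prints the grading for the main rash terms, defines a life-threatening Grade 4 for acneiform rash.

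**Section 6.6.** The lead-in covers all adverse events at least partly related to selumetinib and says that "the following dose reduction/adjustment guidance should be applied unless otherwise specified in the Guidance for management of specific AE (Appendix E". The interruption bullets beneath it name intolerable events of any grade and "Any AE CTCAE grade 3". Restart then requires improvement to Grade 1 or below within 4 weeks of onset and is at a reduced dose. A separate paragraph after Table 7 deals with Grade 4: "Treatment with selumetinib should be permanently discontinued for any CTCAE grade 4 toxicity that is at least partially related to selumetinib". It allows one exception: "interruption of Selumetinib with potential to restart at a reduced dose upon resolution to grade 1 or less may be considered". Each such exception is decided individually, and the study physician has to be consulted.

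**The concern.** A row that starts at Grade 3 and has no top takes in Grade 4. A site with a related Grade 4 acneiform rash can therefore find two different answers on whether to stop and on how to restart. Section 2.3.2 and Section 6.6 both send sites to Appendix E for rash, so Table 19 is a natural place to look.

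The lead-in to Section 6.6 makes this more than untidy labelling. It says Appendix E prevails where it specifies otherwise. If that extends to the Grade 4 paragraph, the plan as written allows a subject, possibly a child as young as 3, to resume the original dose after a life-threatening related rash while still at Grade 2. No default discontinuation would apply, and no consultation with the study physician would be required.

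**Working it through.** No figure in the plan is at issue, so the check sets the two rules side by side for a related Grade 4 rash.

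| Item | Table 19, lower row | Section 6.6, Grade 4 paragraph | Table 19 is |
|---|---|---|---|
| Default action | interruption to be considered | permanent discontinuation | different |
| Grade needed to restart | Grade 2 if tolerable, or lower | Grade 1 or lower | looser |
| Restart dose | original, or consider reduced | reduced | looser |
| Consultation | none stated | study physician, case by case | looser |
| Time limit | 4 weeks | none stated | stricter |

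On the four restart conditions: 3 looser + 1 stricter = 4. The default action differs as well. The tally describes the text and does not measure risk.

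**Does the row reach a real Grade 4 event?** Table 22 prints five terms. Acneiform rash has a Grade 4 entry; pruritus, maculo-papular rash, dry skin and eczema have none. That is 1 of 5, and it is a lower bound, because the table refers other rash terms to CTCAE. Table 23 uses the same open-ended label for paronychia, but Table 24 gives paronychia no Grade 4, so nothing follows there.

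**Which rule prevails?** There are two readings.

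1. *The clause covers all of Section 6.6.* The Grade 4 paragraph follows the lead-in within the same section, and nothing exempts it. Table 19 then replaces the Grade 4 rule for rash.
2. *The clause covers only the interruption guidance.* The bullets directly under it stop at intolerable events and Grade 3, while the Grade 4 rule stands apart and is worded to cover any such toxicity. Section 6.6 then governs, and Table 19 gives sites the wrong instruction for Grade 4.

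Reading 2 is the more natural. At Grade 3, Table 19 works as a declared override: it keeps the 4-week window of the general rule and relaxes the grade and the dose. That suggests it was written against the Grade 3 bullet and not against the Grade 4 paragraph. No sentence in the text available says so.

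**The case against.** The best defence is that the row label is shorthand for severe rash. Taken literally it would also include Grade 5, for which a restart rule is absurd, and the same label is used for paronychia, which has no Grade 4. The linked treatment advice also fits Grade 3 better. Tables 20 and 21 offer topical steroids and oral antibiotics, with broad-spectrum cover in adults if infection is suspected, whereas Grade 4 acneiform rash is defined by extensive superinfection needing intravenous antibiotics. This makes an intended override at Grade 4 unlikely. It does not remove the need to say so, because the remedy for ambiguous shorthand in a dosing table is a clear label.

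Safeguards also exist. The general text that opens Section 8 says: "Immediate safety concerns should be discussed with the sponsor immediately upon occurrence or awareness to determine if the subject should continue or discontinue study treatment". A life-threatening event is reported as serious within 24 hours (Section 8.4.1). Section 7.1 allows treatment to be stopped for an event that the investigator or sponsor judges to contraindicate dosing. Section 8.4.5 points to Section 6.6 for dose modification. These lower the risk, but none states which restart grade, dose or consultation rule applies.

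A reader might infer three stronger things that the Protocol does not support:

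- *That no order of precedence is given.* The lead-in to Section 6.6 gives one in favour of Appendix E. Only its reach to the Grade 4 paragraph is unclear.
- *That the two rules command opposite things.* Section 6.6 itself allows a Grade 4 restart by exception, and Table 19 nowhere forbids permanent discontinuation. They differ in their default and their conditions.
- *That the treatment advice in Tables 20 and 21 is deficient.* Table 20 refers onward to toxicity management guidelines and Table 21 provides for suspected infection. No fault is claimed there.

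**Conclusion.** The point holds as a minor patient-safety correction. Table 19 is uncapped and, read literally, gives related Grade 4 rash a restart rule that differs from Section 6.6 in its default action and in all four restart conditions, three of them looser. Whether the looser rule displaces the Grade 4 safeguards depends on how far the override clause reaches, and the text leaves that open. Either answer calls for a change: one reading weakens the Grade 4 rule for rash, and the other leaves a misleading row in the table.

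The conclusion rests on the literal wording of the label and on the readable text. Some Appendix E flow charts are not reproduced in the copy reviewed, but the rash guidance in E 6 is tabular and legible. The Protocol gives no Grade 4 rash rate, so no number of affected subjects among the planned 32 (16 paediatric + 16 adult) is claimed. Sample size, error rates and endpoint definitions are unaffected.

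**What to change.** Make three edits at the next amendment:

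1. Relabel the lower row of Table 19 as *CTC Grade 2 intolerable or Grade 3*.
2. Add a Grade 4 row that refers to the Section 6.6 Grade 4 rule and its exception.
3. State in Section 6.6 that the clause giving way to Appendix E does not apply to the Grade 4 rule.

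Splitting the matching rows of Tables 20 and 21 in the same way is optional.

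The cost is one label, one row and one sentence, with no added assessments. If the sponsor does intend Appendix E to override Section 6.6 at Grade 4, the third edit would change the rule and not merely clarify it, so that intention should be confirmed first.

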8.4.5 Management of investigational product-related toxicities

Recommendations for the management or investigation of specific AEs is provided in Appendix E.

Dose modification guidance is included in Section 6.6.

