Appendix E Guidance for management of specific adverse events in adults and paediatric patients

E 1 Management of Left Ventricular Ejection Fraction (LVEF) Reduction (asymptomatic) or Left Ventricular Systolic Dysfunction (LVSD)

		-				_	
Table 15	CTCAE (version :	5) gra	ding for	·LVEF	reduction	and LVSD
		VU SION	.,	ang ivi		I COMPOSITION	

CTCAE term	Grade 1	Grade 2	Grade 3	Grade 4	Grade 5
Ejection fraction decreased	-	Resting ejection fraction (EF) 50 - 40%; 10 - 19% drop from baseline	Resting ejection fraction (EF) 39 - 20%; >=20% drop from baseline	Resting ejection fraction (EF) <20%	-
Left ventricular systolic dysfunction	-	-	Symptomatic due to drop in ejection fraction responsive to intervention	Refractory or poorly controlled heart failure due to drop in ejection fraction; intervention such as ventricular assist device, intravenous vasopressor support, or heart transplant indicated	Death

E 2 Management of creatine kinase (CK) elevation

Table 16	CTCAE (version 5	b) grading for CPK	increased and	rhabdomyolysis
----------	------------------	--------------------	---------------	----------------

CTCAE term	Grade 1	Grade 2	Grade 3	Grade 4	Grade 5
CPK increased	>ULN - 2.5 x ULN	>2.5 x ULN - 5 x ULN	>5 x ULN - 10 x ULN	>10 x ULN	-
Rhabdomyolysi s	Asymptomatic, intervention not indicated; laboratory findings only	Non-urgent intervention indicated	Symptomatic, urgent intervention indicated	Life-threatening consequences; dialysis	Death

E 3 Management of Retinal Pigment Epithelial Detachment (RPED), Central Serous Retinopathy (CSR) and Retinal Vein Occlusion (RVO)

CSR=central serous retinopathy; RPED=retinal pigment epithelial detachment; RVO=retinal vein occlusion.

E 4 Management of diarrhoea

Table 17 CTCAE (version 5) grading for diarrhoea

Grade 1	Increase of <4 stools per day over baseline; mild increase in ostomy output compared to baseline.
Grade 2	Increase of 4 to 6 stools per day over baseline; moderate increase in ostomy output compared to baseline; limiting instrumental ADL (Instrumental ADL refer to preparing meals, shopping for groceries or clothes, using the telephone, managing money, etc).
Grade 3	Increase of \geq 7 stools per day over baseline; hospitalisation indicated; severe increase in ostomy output compared to baseline; limiting self care ADL (self care ADL refer to bathing, dressing and undressing, feeding self, using the toilet, taking medications, and not bedridden).

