CTC Grade 2 Rash (Intolerable) Or CTC Grade≥3	Apply a moderate potency topical steroid* and initiate an oral antibiotic***. Topical antibiotics should be discontinued before initiation of oral antibiotics. Follow toxicity management guidelines.	 Clindamycin gel, lotion, or solution. ***Oral tetracyclines e.g. doxycycline or minocycline (dosage regimens as per local guidelines). Doxycycline should be taken with food to avoid nausea. Minocycline should only be used if doxycycline is not tolerated. (tetracyclines should be avoided in children younger than 8 years because of risk to tooth discoloration).

Table 21 Rash - Adult Treatment Recommendations

Recommendations to start on day 1 of treatment with selumetinib and continue for the whole duration of treatment.

- Apply a skin moisturiser (thick, alcohol-free) at bedtime.
- Avoid excessive exposure to sunlight.
- Avoid the use of topical retinoids or benzoyl peroxide, as these are not recommended.

Severity	Treatment Recommendations	Note		
CTC Grade 1 rash	Apply a mild/moderate strength topical steroid and/or topical antibiotic.	Example antibiotics and topical steroids (dosage regimens as per local		
CTC Grade 2 rash (Tolerable)	Apply a moderate strength topical steroid and consider an oral antibioticApply moderate strength topical steroid and consider an oral antibiotic. If an infection is suspected, consider otherbebroad spectrum antibiotic cover	guidelines): Topical steroids moderate strength e.g:		
CTC Grade \geq 3 rash or a CTC Grade 2 rash considered by the patient to be intolerable		Topical antibiotics e.g: Clindamycin, Erythromycin, Metronidazole, Silver sulphadiazine.		
r		Oral antibiotics e.g: Doxycycline, Minocycline, Oxytetracycline.		

Table 22CTCAE (version 5) grading for Rash relevant terms

(For other specific rash term, please refer to CTCAE guideline)

CTCAE term	Grade 1	Grade 2	Grade 3	Grade 4	Grade 5
Pruritus	Mild or	Widespread and	Widespread and	-	-
	localized;	intermittent; skin	constant;		
	topical	changes from	limiting self		
	intervention	scratching (e.g.,	care ADL** or		
	indicated	edema, papulation,	sleep; systemic		
		excoriations,	corticosteroid or		
		lichenification,	immunosuppres		
		oozing/crusts); oral	sive therapy		
		intervention	indicated		
		indicated; limiting			
		instrumental ADL*			

CTCAE term	Grade 1	Grade 2	Grade 3	Grade 4	Grade 5

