- Patients with a healthy mouth may use non alcoholic mouthwash 4 to 6 times daily (e.g. after each meal), or according to the instructions, during the study.
- Saline mouthwashes (Sodium chloride 0.9%) are preferred to alcohol-based mouth washes in cases of stomatitis, and should be used at a different time than toothbrushing (e.g. after tea).
- Use of a mouthwash immediately after selumetinib intake is recommended.
- The tongue can be gently brushed (if not sore) with a soft toothbrush.
- Patients with, or at risk of, stomatitis should not use commercial/over-the-counter mouthwashes because of the alcohol content and astringency. Chlorhexidine mouthwashes are not recommended for the treatment of established stomatitis.
- The mouth should be regularly inspected by the patient and healthcare professionals.
- Teeth should be brushed twice daily with a fluoride toothpaste and soft toothbrush, in the morning before breakfast and last thing in the evening before bed, about 30 minutes after eating. The toothbrush should be replaced regularly (at least every 3 months). Patients with stomatitis should change their toothbrush every 4 6 weeks.
- Consider culture to rule out herpes simplex.
- Consider treating stomatitis at an early stage (CTCAE grade 1) or as soon as the patient complains of a sore mouth. Consider using an oral topical analgesic, with or without topical steroids, depending on the patient's clinical condition and the local standard medical practice.

CONFIDENTIAL AND PROPRIETARY 124 of 183

E 8 Management of Paronychia

Severity	Management STEP 1	Management STEP 2
CTC Grade 1 or 2 Tolerable Paronychia	Continue Selumetinib treatment and monitor as clinical indicated.	-
	Manage paronychia as per treatment recommendations.	
CTC Grade 2 Intolerable or CTC Grade≥3	Consider Selumetinib dose interruption. Consider referral to a dermatologist. Manage paronychia as per treatment recommendations.	If paronychia has improved to Grade 2 tolerable or less within 4 weeks, re-start selumetinib at original dose or consider reduced dose.

Table 23Management of Paronychia

Table 24CTCAE (version 5) grading for paronychia

CTCAE term	Grade 1	Grade 2	Grade 3	Grade 4	Grade 5
Paronychia	Nail fold	Local intervention indicated; oral	Operative	-	-
	edema or	intervention indicated (e.g.,	intervention		
	erythema;	antibiotic, antifungal, antiviral);	indicated; IV		
	disruption	nail fold edema or erythema with	antibiotics		

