	of the	pain; associated with discharge or	indicated;		
	cuticle	nail plate separation; limiting	limiting self		
		instrumental ADL*.	care ADL**.		

*Instrumental ADL refer to preparing meals, shopping for groceries or clothes, using the telephone, managing money, etc.

**Self care ADL refer to bathing, dressing and undressing, feeding self, using the toilet, taking medications, and not bedridden.

Table 25 Treatment Recommendations for AE Paronychia*

Severity	Treatment Recommendations					
CTCAE grade 1	Treat the affected area by soaking in vinegar solution twice daily (1 part vinegar to 2 parts water) + Topical Antibiotic mupirocin twice daily.					
CTCAE grade 2	Treat the affected area by soaking in vinegar solution twice daily (1 part vinegar to 2 parts water) + Systemic antibiotic (Keflex, Clindamycin)+ high potency steroid (0.05% clobetasol ointment covered with saran wrap OR flurandrenolide tape (cordran tape) applied at bedtime. This should be removed in morning.					
CTCAE grade 3	If severe, seek consult for incision & drainage or surgical management.					
* If granulation tissue present, consider use of silver nitrate under supervision.						

For patients who do not undergo drainage, silver nitrate may be used, as well as topical bactroban, steroids, and/or antifungals. Silver nitrate is only of value when there is open inflamed skin or granulation tissue (e.g. pyogenic-granuloma-like lesions). If the periungual CONFIDENTIAL AND PROPRIETARY 125 of 183

skin is swollen but intact (whether infectious or non-infectious), silver nitrate is not recommended.

Patients should be cautioned to avoid trauma to the area. Podiatry consult may be considered for partial nail removal.

Patients who undergo incision and drainage and are found to have no infectious organisms on culture, should be treated as above. If infection is identified, patients may be treated with systemic antibiotics (oral tetracyclines).

If paronychia recurs or develops in other fingers or toes, Flurandrenolide (e.g. Cordran) tape or topical steroid cream such as triamcinolone can be used in the morning and Bactroban and Nizoral topical ointments in the evening.

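### Appendix E 8 offers oral tetracyclines for infected paronychia with no age limit, while the Table 20 note in the same appendix says to avoid them under 8 years

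*Protocol*

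**What the plan says.** The title of Appendix E gives its scope as "Guidance for management of specific adverse events in adults and paediatric patients".

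The two relevant parts are organised differently:

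- **E 6, rash.** Table 19 splits the advice by age: "Manage rash as per paediatric or adult treatment recommendations". The paediatric recommendations are in Table 20, whose note names doxycycline and minocycline and adds that "tetracyclines should be avoided in children younger than 8 years because of risk to tooth discoloration".
- **E 8, paronychia.** Table 23 does not split the advice: "Manage paronychia as per treatment recommendations". One table (Table 25) and one block of text serve all ages. The grade 2 row of Table 25 lists "Systemic antibiotic (Keflex, Clindamycin" as systemic options. The grade 3 row gives only a consult for drainage or surgery. The text on drained patients then has two branches. If the culture is negative: "Patients who undergo incision and drainage and are found to have no infectious organisms on culture, should be treated as above". If it is positive: "If infection is identified, patients may be treated with systemic antibiotics (oral tetracyclines".

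The paediatric cohort runs from 3 years to under 18 (section 5.1, criterion 3), with at least 6 subjects aged 3 to 11 and at least 6 aged 12 to 17.

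**The concern.** The protocol states an age rule for a drug class in one part of the appendix and names the same class without the rule in another. A site treating an infected nail fold would read E 8. Nothing there points to a footnote under the paediatric rash table.

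What is at stake is the safety of individual children: a child aged 3 to 7 could be given a tetracycline on the protocol's own advice, against the protocol's own caution about tooth discoloration. The statistical content of the trial is not touched.

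**Working it through.** The protocol gives no figure on this point to reproduce, so the check is mainly a comparison of texts.

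**1. Does the E 8 sentence reach children under 8?** Yes. The appendix covers both cohorts, E 8 speaks of patients without distinction, and criterion 3 admits children from age 3. The protocol also plans for the youngest ages, with FLACC for 3-year-olds and PedsQL forms for ages 3 to 4 and 5 to 7. The entry floor on body surface area does not remove them. Under the protocol's formula for children of 30 kg or less, BSA = 0.035 × weight + 0.1, so a BSA of 0.55 m² corresponds to (0.55 − 0.1) / 0.035 = 12.9 kg.

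**2. Is the sentence restricted anywhere else?** No. E 8 has no age qualifier and no cross-reference to Table 20. Sections 6.5.2, 6.6 and 8.4.5 add none.

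**3. Are alternatives offered at that point?** Not in the sentence itself. Keflex and clindamycin stand in the grade 2 row of Table 25. The reference back to earlier treatment is given for the culture-negative branch only. The infected branch names tetracyclines alone.

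**4. The texts side by side for a child aged 3 to 7**

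| Place | Condition | Advice on tetracyclines |
|---|---|---|
| E 6, Table 20 note | Rash, paediatric | Avoid under 8 years |
| E 8, text after Table 25 | Paronychia, drained and infected, all ages | May be used; no age stated |

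**5. How many children could be concerned?** The protocol gives no rate of drained and infected paronychia, so exposure cannot be estimated. Enrolment can only be bounded:

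- Planned children: about 16.
- At least 6 aged 12 to 17, so at most 16 − 6 = 10 aged 3 to 11.
- Aged 3 to 7: between 0 and 10, since the 3 to 11 group is not subdivided.

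Section 4.3 reports that the supporting paediatric study at the same dose enrolled children from 3.5 to 17.4 years, median 10.2. That shows children under 8 have entered such a study. It does not give their share.

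**The case against.** The strongest reply is that this is a caution not repeated, rather than a contradiction. The Table 20 note is worded generally and its reason, tooth discoloration, has nothing to do with rash. Read as a whole, the appendix yields one consistent rule: tetracyclines may be used, except under 8. Sites are likely to know the note, because section 2.3.1 lists acneiform rash among the most frequent related events.

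Several safeguards also come into play. E 8 says only that tetracyclines may be used. Section 8.4.5 presents the appendix as "Recommendations for the management or investigation of specific AEs", and section 6.5.2 leaves other medication to the investigator. Table 23 suggests considering dermatology referral for intolerable grade 2 or worse, Table 24 counts an indication for intravenous antibiotics among its grade 3 criteria, and a culture result would inform the choice. The child must also be 3 to 7, drained and infected, which may never happen in about 16 children. The need to swallow whole capsules works against enrolling the youngest.

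Most of this stands, and it is why the point is minor. It does not remove the gap. The note belongs to a paediatric rash table to which E 8 does not direct the reader. The sponsor did not rely on general knowledge in Table 20, where the limit is written next to the drug, and the same care is due in E 8. A culture identifies the organism and does not address a risk that depends on age.

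**Conclusion.** The concern holds. As written, E 8 permits for children aged 3 to 7 a drug class that the same appendix says to avoid at that age. It is a minor inconsistency in supportive-care guidance, worth correcting but not urgent.

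The conclusion rests on the protocol text alone: the all-ages scope of Appendix E, the entry age of 3, the Table 20 note and the unqualified E 8 sentence. The range of 0 to 10 children is a ceiling on enrolment, not on exposure. It assumes exactly 16 children, where the protocol says approximately 16. Whether any child would receive a tetracycline because of this sentence is unknown.

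**What to change.** Reword the one sentence in Appendix E 8, for example: *Where infection is found, a systemic antibiotic guided by culture may be given; oral tetracyclines only from 8 years of age, and in younger children a non-tetracycline agent such as those named in Table 25.*

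Both Table 25 agents are already in E 8 for the same condition. Neither is among the CYP inhibitors in Table 32, which does list erythromycin and clarithromycin, so naming them also steers sites away from antibiotics the protocol wants avoided.

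The cost is one sentence, which can go into the next amendment. No visits, data, subjects or analyses change, and Table 20 stays as it is.
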